1.1. Study Objectives

The purpose of this study is to obtain data on the 24-hour IOP lowering effect at Week 8 of Bimatoprost SR treatment, with safety assessed until Month 12. Each study objective is presented below with associated information.

Table 1-1 Study Objectives and Corresponding Endpoints

Objectives	Endpoints/Measures

Efficacy:
 
Primary
 
• To evaluate the 24-hour IOP-lowering effect of Bimatoprost SR in participants with OAG or OHT 
Secondary
 
• To evaluate the change in diurnal variation of IOP in eyes treated with Bimatoprost SR 
Other
 
• To evaluate the IOP-lowering effect of Bimatoprost SR	
• Time-matched IOP change from Baseline Sleep Lab visit at Week 8 Sleep Lab visit in Bimatoprost SR-treated eyes• Change from baseline in range of IOP in eyes treated with Bimatoprost SR at Week 8 Sleep Lab visit• Hour 0 IOP change from baseline through Month 12• Time to initial use of nonstudy IOP-lowering treatment

Safety:
 
• To evaluate the safety of Bimatoprost SR in participants with OAG or OHT	
• AEs, visual fields, visual acuity, macroscopic bulbar conjunctival hyperemia, slit-lamp biomicroscopic assessments, dilated ophthalmoscopic assessments (including optic disc assessment), contact ultrasound pachymetry, gonioscopy, specular microscopy

1.2. Study Design

This study is a multicenter, open-label, Phase 3b study in participants with OAG or OHT. Approximately 35 participants will be enrolled: 25 to 30 in the Bimatoprost SR cohort (to achieve a minimum total of 20 evaluable participants at baseline and Week 8 to evaluate the 24-hour IOP-lowering effect of Bimatoprost SR, assuming a premature discontinuation rate of up to 33%), and 5 in the LUMIGAN® 0.01% (bimatoprost ophthalmic solution) cohort. Participants who prematurely discontinue from the study will not be replaced.

1.2.1. Intervention Group and Study Duration

Participants in the Bimatoprost SR cohort will receive a 10 µg implant in the study eye on Day 1, and the fellow eye will receive standard of care treatment (provided that there is no known crossover effect of the fellow eye's standard of care treatment to the study eye) for the duration of the study. At selected site(s) an additional cohort of participants will be enrolled and assigned to receive topical LUMIGAN 0.01% in the study eye (once daily, at 20:00 ± 1 hour, starting with the evening dose on Day 1), and standard of care treatment in the fellow eye (provided that there is no known crossover effect of the fellow eye's standard of care treatment to the study eye) for the duration of the study. Participants will be assigned to the Bimatoprost SR cohort or LUMIGAN 0.01% cohort [REDACTED].

The participant and investigator will not be masked to the study treatment assignment for the duration of the study. Site staff collecting 24-hour IOP measurements at Sleep Lab visits will be masked to the study treatment and study eye.

Study Eye Treatment	Fellow Eye Treatment
Bimatoprost SR 10 µg or LUMIGAN 0.01% ^a (at selected site[s])	Standard of Care

^a Participants will begin self-administration of LUMIGAN 0.01% in the study eye once daily in the evening (20:00 ± 1 hour) starting with the evening dose on Day 1, and will continue self-administration daily through the duration of the study.

The duration of the study for each participant is approximately 15 months, consisting of a screening period of up to 60 days before washout, washout period of up to 42 days before Baseline, and 12 months of follow-up.

[figure not shown]
Participants who complete all regularly scheduled study visits should have 9 study office visits, 2 sleep lab visits, and 1 phone call. The schedule includes the following:

- Screening (up to 60 days); Washout Period of up to 42 days; and Baseline (Office visit and Sleep Lab visit)
- Day 1; Day 2 Safety visit
- Day 8 phone call
- Weeks 8 (Office and Sleep Lab visits) and Week 16; and Months 6, 9, and 12/Study Exit visits.

1.2.2. Schema

The study schema is presented in [Figure 1–1](#).

Figure 1–1 Study Schema

^a 24-Hour IOP monitoring

^b Bimatoprost SR administration or, at selected sites, participants assigned to LUMIGAN will begin self-administration of LUMIGAN once daily in the evening in the study eye starting at 20:00 ± 1 hour.

^c Phone call

1.2.3. Schedule of Activities (SoA)

Table 1-2 Schedule of Activities – Screening through Week 8

Visit	Screening		Baseline		Day 1	Day 2 Safety Visit	Day 8 Phone Call	Week 8		
			Office Visit	Sleep Lab Visit ^d				Office Visit	Sleep Lab Visit ^d	
Visit Windows	Up to 60 days ^a	Washout ^b up to 42 days	-7 days from Sleep Lab Visit ^c				+14 days	-7 days from Sleep Lab Visit ^c	± 7 days	
Informed Consent/Authorization	X									
Demographic Data	X									
Medical/Ophthalmic History	X		X							
Adverse Events	X		X	X	X	X	X	X	X	
Concomitant Medications/Procedures	X		X	X	X	X	X	X	X	
Alcohol/Caffeine/Smoking/Sleep	X			X					X	
Physical Examination	X									
Vital Signs (at rest ≥ 5 minutes)	X		X	X	X	X		X	X	
Pregnancy Test ^e			X							
Blood and Urine Sample Collection ^f	X									
Ocular Examinations in bold should be performed in the order shown										
Pre-Hour 0 Exam (perform before Hour 0 IOP):										
Macroscopic Conjunctival Hyperemia Assessment	OU	Washout ^b up to 42 days	OU			OU		OU		
Manifest Refraction^g	OU		OU							
Best-Corrected Visual Acuity	OU		OU		OU		OU			
Intraocular Pressure Measurement Hour 0	OU		OU		OU		OU			
Anterior Segment Imaging ^h (may perform any time after Hour 0 IOP)	OU		OU				OU			
Non-contact Exams (may perform in any order at any time before gonioscopy, including prior to H0 IOP)										
Visual Field ⁱ	OU	Washout ^b up to 42 days	OU			OU		OU		
Specular Microscopy ^j	OU		OU							
Biomicroscopy	OU		OU		OU		OU			
Gonioscopy/Angle Assessment	OU		OU				OU			
Pachymetry: (may be performed any time after non-contact exams)	OU		OU							
Pupil Dilation (may perform exams in any order)	OU	Washout ^b up to 42 days	OU							
Dilated Ophthalmoscopy	OU		OU							
Optic Disc Examination	OU		OU							

Visit	Screening		Baseline		Day 1	Day 2 Safety Visit	Day 8 Phone Call	Week 8	
			Office Visit	Sleep Lab Visit ^d				Office Visit	Sleep Lab Visit ^d
			-7 days from Sleep Lab Visit ^c				+14 days	-7 days from Sleep Lab Visit ^c	± 7 days
Visit Windows	Up to 60 days^a								
Determination of Eligibility	X		X						
Contact IWRS ^k	X		X		X				
24-Hour IOP Measurements ^l				OU					OU
Study Treatment ^m					SE				

Hour 0 = 08:00 ± 1 hour assessed with a Goldmann applanation tonometer

- a Eligibility criteria may be rechecked at any time prior to and during washout, at the discretion of the investigator.
- b Washout in both eyes may begin after all screening procedures have been completed.
- c Office visit procedures may be performed up to 7 days prior to Sleep Lab visit.
- d Perform 24-hour Sleep Lab visit on a different day from all other Office visit study procedures.
- e At sites where required by local institution or health authority, a serum test may be done, with negative results for all tests confirmed prior to the time of Bimatoprost SR administration. Pregnancy testing at Baseline is required regardless.
- f Blood and urine samples are collected only at Screening unless a retest is necessary.
- g Manifest refraction will be used to provide a correction for best-corrected visual acuity testing. At all study visits, if there is a 2-line or more reduction in visual acuity from the last best-corrected visual acuity performed, a repeat manifest refraction in both eyes and best-corrected visual acuity will be performed.
- h At selected sites/selected participants only, anterior segment imaging may be performed in both eyes of consenting participants using Allergan-approved instruments.
- i For a given participant, the same test methodology must be used for all visual fields performed at Screening, Baseline, and throughout the study.
- j For a given participant, the same specular microscope model and analysis methodology must be used at Screening, Baseline, and throughout the study.
- k Screening: participant number; Baseline: Hour 0 IOP; Day 1: enrollment after eligibility confirmation (may be done at end of Baseline visit if needed)
- l All 24-hour Sleep Lab visit IOP exams will be performed with an Allergan-specified tonometer. Diurnal IOP measurements will be taken supine ≥ 5 minutes at rest then sitting ≥ 5 minutes at rest at 8:00 ± 30 min, 10:00 ± 30 min, 12:00 ± 30 min, 14:00 ± 30 min, 16:00 ± 30 min, 18:00 ± 30 min, 20:00 ± 30 min, and 22:00 ± 30 min. Nocturnal IOP measurements will be taken supine only ≥ 5 minutes at rest 00:00 ± 30 min, 02:00 ± 30 min, 04:00 ± 30 min, and 06:00 ± 30 min. Please see Procedure Manual for details.
- m Bimatoprost SR is administered on Day 1. At selected sites, participants assigned to LUMIGAN 0.01% will begin self-administration of LUMIGAN 0.01% once daily in the evening in the study eye starting with the evening dose on Day 1. Those participants will continue self-administration of LUMIGAN 0.01% once daily in the evening (20:00 ± 1 hour) throughout the study.

Table 1-3 Schedule of Activities – Week 16 through Month 12/Study Exit

Visit	Week 16	Month 6	Month 9	Month 12/ Study Exit
Visit Windows	± 4 days	± 14 days	± 14 days	± 14 days
Adverse Events	X	X	X	X
Concomitant Medications/ Procedures	X	X	X	X
Vital Signs (at rest \geq 5 minutes)	X	X	X	X
Pregnancy Test				X
Ocular Examinations in bold should be performed in the order shown				
Pre-Hour 0 Exams (perform before Hour 0 IOP):				
Macroscopic Conjunctival Hyperemia Assessment	OU	OU	OU	OU
Best-Corrected Visual Acuity	OU	OU	OU	OU
Intraocular Pressure Measurement Hour 0	OU	OU	OU	OU
Anterior Segment Imaging ^a (may perform any time after Hour 0 IOP)		OU		OU
Non-contact Exams (may perform in any order at any time before gonioscopy, including prior to H0 IOP)				
Visual Field ^b		OU		OU
Manifest Refraction ^c				OU
Specular Microscopy ^d	OU	OU	OU	OU
Biomicroscopy	OU	OU	OU	OU
Gonioscopy/Angle Assessment	OU	OU	OU	OU
Pachymetry: (may be performed any time after non-contact exams)	OU	OU	OU	OU
Pupil Dilation (may perform exams in any order)				OU
Dilated Ophthalmoscopy				OU
Optic Disc Examination				OU
Contact IWRS ^e				X

Hour 0 = 08:00 \pm 1 hour assessed with a Goldmann applanation tonometer

- a At selected sites/selected participants only, anterior segment imaging may be performed in both eyes of consenting participants using Allergan-approved instruments.
- b For a given participant, the same test methodology must be used for all visual fields performed at Screening, Baseline, and throughout the study.
- c Manifest refraction will be used to provide a correction for best-corrected visual acuity testing. At all study visits, if there is a 2-line or more reduction in visual acuity from the last best-corrected visual acuity performed, a repeat manifest refraction in both eyes and best-corrected visual acuity will be performed.
- d For a given participant, the same specular microscope model and analysis methodology must be used at Screening, Baseline, and throughout the study.
- e Contact IWRS for study completion or participant discontinuation/withdrawal.

1.2.4. End of Study Definition

The end of the study is defined as the date of the last visit of the last participant in the study or last scheduled procedure shown in the SoA for the last participant in the study.

A participant assigned and treated with Bimatoprost SR is considered to have completed the study if he/she has completed all visits of the study to Month 12. At the Month 12/Study Exit visit, if the investigator determines that any safety concerns warrant participant follow-up, the participant may be followed post exit until safety concerns are resolved based on the investigator's discretion. Participants assigned and treated with LUMIGAN 0.01% may early

exit the study after completion of the Week 8 Sleep Lab visit, if there are no safety concerns in the opinion of the investigator. For the LUMIGAN cohort, an exit visit will be performed after the Week 8 Sleep Lab visit where all assessments scheduled for the Month 12/Study Exit visit will be performed.

2. Statistical Hypotheses

There are no statistical hypotheses for this study.

3. Sample Size Determination

The sample size is based on practical considerations. Approximately 35 participants will be enrolled: 25 to 30 in the Bimatoprost SR cohort and 5 in the LUMIGAN 0.01% cohort.

Twenty-five to 30 participants will be enrolled in the Bimatoprost SR cohort to achieve a minimum total of 20 evaluable participants, defined as participants with sufficient data at baseline and Week 8 to evaluate the 24-hour IOP-lowering effect of Bimatoprost SR. This assumes a premature discontinuation rate of up to 33%. Participants who prematurely discontinue from the study will not be replaced. Participants will be assigned to the Bimatoprost SR or LUMIGAN 0.01% cohort [REDACTED].

4. Populations for Analysis

4.1. Safety Analysis Set (SAF)

All participants who have received study intervention (ie, Bimatoprost SR administration or LUMIGAN 0.01%) will contribute to the SAF. All safety data collected from these participants will be included in the SAF.

4.2. Full Analysis Set (FAS)

All participants who have received study intervention (ie, Bimatoprost SR administration or LUMIGAN 0.01%) with at least 1 postbaseline IOP assessment (including an unscheduled visit assessment) on the study eye will contribute to the FAS. All efficacy data collected from these participants will be included in the FAS with the following exception:

- To avoid confounding of efficacy data, IOP measurements obtained after initiating the use of non-study rescue IOP-lowering treatment (medication[s] or procedure[s] or both) in an eye will be excluded from FAS.

5. Statistical Analyses

5.1. General Considerations

Two database locks are planned for this study. The first database lock (referred to as primary DBL), for the primary and secondary efficacy endpoint analysis, will occur when 100% of participants have completed the primary visit (ie, Week 8 Sleep Lab visit) or prematurely discontinued prior to the Week 8 Sleep Lab visit. Similarly, the second database lock (referred to as final DBL) for the full study database will occur after all participants have completed the study at Month 12 or prematurely discontinued from the study. Analyses will be performed after each lock and this SAP will cover both primary and final analysis.

5.1.1. Statistical Notation and Presentation

Continuous variables will be summarized by cohort (Bimatoprost SR or LUMIGAN 0.01%) for number of participants, mean, standard deviation (SD), median, first quartile, third quartile, minimum, and maximum values. Categorical variables will be summarized by frequency counts and percentage of participants within each treatment cohort.

All statistical analyses will be performed using Statistical Analysis Software (SAS®) version 9.4.

5.2. Participant Disposition

Number of participants screened for the study will be provided. Counts of the participants in the two analysis populations will be summarized by treatment cohorts. The number and percentages of participants who completed or discontinued from the study in the eCRF open label form, as well as the discontinuation reasons, will be summarized by treatment cohorts.

5.3. Efficacy Analysis

The efficacy analyses will be based on the FAS population. Data handling conventions are described in Section 6.3 Appendix 3.

Time-matched IOP will be collected at 12 timepoints across the 24-hour period (08:00, 10:00, 12:00, 14:00, 16:00, 18:00, 20:00, 22:00, 00:00, 02:00, 04:00 and 06:00). The diurnal IOP will be collected between 08:00 to 22:00 and the nocturnal IOP will be collected between 00:00 and 06:00. The diurnal IOP will be performed in supine and sitting positions while the nocturnal IOP will be performed only in a supine position. The primary and secondary efficacy analysis will be performed based on the habitual IOP (the diurnal IOP in a sitting position and the nocturnal IOP in a supine position).

Hour 0 IOP examinations will be scheduled at $08:00 \pm 1$ hour and all Hour 0 IOP examinations will be performed with the participants in a sitting position.

5.3.1. Analysis Endpoint(s)

- The primary efficacy endpoint is the time-matched IOP change from baseline at the Week 8 Sleep Lab visit from the 24-hour IOP data collected at the Baseline Sleep Lab visit in the study eye for the Bimatoprost SR cohort.
- The secondary efficacy endpoint is the change from baseline in range of IOP in eyes treated with Bimatoprost SR at Week 8 Sleep Lab visit.
- Other efficacy endpoints include:
 - Time-matched IOP change from baseline in a supine position.
 - Hour 0 IOP change from baseline through Month 12.
 - Time to initial use of nonstudy IOP-lowering treatment.

Refer to Section 6.3 Appendix 3 for details on IOP measurement conventions and corresponding time windows.

5.3.2. Primary Efficacy Analyses

The habitual IOP values at various hours of the Baseline Sleep Lab visit will be considered as the time-matched baseline values for the corresponding timepoints of Week 8 Sleep Lab visit. For example, the habitual IOP time-matched change from baseline at timepoint 06:00 of Week 8 Sleep Lab visit will be calculated as: habitual IOP at timepoint 06:00 of Week 8 Sleep Lab visit – habitual IOP at timepoint 06:00 of Baseline Sleep Lab visit.

The habitual IOP raw values and the corresponding time-matched change from baseline in habitual IOP will be summarized descriptively by visit and by timepoint for the study eye in the Bimatoprost SR and Lumigan 0.01% cohorts as well as for the fellow eye in the pooled treatment cohorts. Ninety-five percent CIs based on a paired t-test statistic will be provided for the mean time-matched habitual IOP change from baseline at 12 timepoints across the 24-hour period for the study eye in the Bimatoprost SR cohort.

The mean habitual IOP and the mean time-matched habitual IOP change from baseline across the 24-hour period will be presented graphically with the timepoint of IOP measurements on the x-axis for the study eye in the Bimatoprost SR cohort. The diurnal/wake period and nocturnal/sleep period within the 24-hour measurement period will be clearly marked in the figure.

5.3.3. Secondary Efficacy Analyses

The habitual IOP fluctuation will be evaluated by the range of habitual IOP values for each participant collected from the Sleep Lab visit during diurnal/wake period and nocturnal/sleep period, as well as over a 24-hour period in the Bimatoprost SR and Lumigan 0.01% cohorts. Descriptive summary statistics on the analysis variable (range of IOP) at baseline and Week 8, as well as its corresponding changes from baseline at Week 8, will be presented by treatment cohorts for the study eye and the pooled treatment cohorts for the fellow eye. The same analysis will be performed for the IOP in a supine position.

5.3.4. Other Efficacy Analyses

Other efficacy analyses will include IOP analysis by body positions, time-to-event of the initial use of nonstudy IOP-lowering treatment and Hour 0 IOP analysis in a sitting position.

5.3.4.1. IOP Analysis by Body Positions

The same analysis of the habitual IOP analysis will be performed for the IOP in a supine position for the study eye in Bimatoprost SR and Lumigan 0.01% cohorts as well as for the fellow eye in the pooled treatment cohorts. For the diurnal IOP, the mean difference of time-matched IOP between sitting and supine positions will be summarized.

For IOP in a supine position, the mean IOP and the mean time-matched IOP change from baseline across the 24-hour period will be presented graphically.

5.3.4.2. Time-to-Event Analysis

Time to the event of the initial use of nonstudy rescue IOP lowering treatment (medication and/or procedure) in the study eye from the date of Bimatoprost SR treatment will be estimated using Kaplan-Meier (KM) method with graphical display.

Time to initial use of nonstudy rescue IOP lowering treatment = (Date of initial use of non-study IOP-lowering treatment – Date of the Bimatoprost treatment) + 1.

In the calculation of time to initial use of nonstudy rescue IOP lowering treatment, if a participant did not use any nonstudy rescue IOP lowering treatment in the study eye, then the event (initial use of nonstudy rescue IOP lowering treatment) time will be censored at the study exit date or the last visit date if the study exit date is not available.

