#### **2.2.4. Clinical Studies with Bimatoprost SR**

Study 192024-041D was a Phase 1/2 paired-eye comparison study evaluating the safety and efficacy of 4 dose strengths of Bimatoprost SR (6, 10, 15, or 20 µg [2 x10 µg implants]), as single or repeat administrations in 1 eye (study eye), versus the use of topical LUMIGAN 0.03% once daily in the contralateral eye (nonstudy eye). The objective of the study was to evaluate the safety and IOP-lowering efficacy of Bimatoprost SR in participants with OAG.

A total of 109 participants received at least a single administration of Bimatoprost SR, and 24 participants received a repeat administration of their initial Bimatoprost SR dose strength. A trend in dose response was observed across the 4 dose strengths that were tested. Data collected in this study suggested that the implant would provide topical prostaglandin analog-like efficacy up to 3 to 4 months after implantation in the majority of participants. Data following the second administration in the retreated participants showed similar IOP-lowering efficacy to that observed following the first administration of Bimatoprost SR.

There have been 2 generations of the Bimatoprost SR implant: the original Generation 1 formulation, and Generation 2, which is the formulation currently used in the Phase 3 studies. Among all Generation 2 dose strengths, most participants (> 66%) were still maintained on monotherapy with the initial Bimatoprost SR implant by Month 6. Additionally, at least 33% of participants had not received rescue topical IOP-lowering medication or a second Bimatoprost SR administration by Month 12. At Month 24, at least 23% of participants had not received rescue IOP-lowering treatment or a second administration of Bimatoprost SR.

Bimatoprost SR showed an acceptable safety profile with single and repeat administrations in Study 192024-041D. Most AEs were ocular, mild or moderate in severity, occurred within the first 2 days after Bimatoprost SR administration, and were considered related to the study drug administration procedure. There were no reports of serious study drug-related AEs, and no new safety concerns were observed after the second treatment that were not already known from the initial administration of Bimatoprost SR. Please refer to the investigator's brochure for details on reported safety findings.

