### 3. Objectives and Endpoints

Objectives	Endpoints/Measures

Efficacy:
 
Primary
 
 
• To evaluate the 24-hour IOP-lowering effect of Bimatoprost SR in participants with OAG or OHT
 
 
Secondary
 
 
• To evaluate the change in diurnal variation of IOP in eyes treated with Bimatoprost SR
 
 
Other
 
 
• To evaluate the IOP-lowering effect of Bimatoprost SR
 
	
 
• Time-matched IOP change from Baseline Sleep Lab visit at Week 8 Sleep Lab visit in Bimatoprost SR-treated eyes
 
• Change from baseline in range of IOP in eyes treated with Bimatoprost SR at Week 8 Sleep Lab visit
 
• Hour 0 IOP change from baseline through Month 12
 
• Time to initial use of nonstudy IOP-lowering treatment
 

Safety:
 
 
• To evaluate the safety of Bimatoprost SR in participants with OAG or OHT
 
	
 
• AEs, visual fields, visual acuity, macroscopic bulbar conjunctival hyperemia, slit-lamp biomicroscopic assessments, dilated ophthalmoscopic assessments (including optic disc assessment), contact ultrasound pachymetry, gonioscopy, specular microscopy
 

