#### **6.5.3. Rescue Medicine**

In the event that the study eye IOP does not meet or does not maintain IOP-lowering expectations, rescue IOP-lowering treatment (medication[s] or procedure[s] or both) can be initiated at the investigator's discretion. Inadequate control of IOP should be confirmed at a subsequent visit (scheduled or unscheduled visit) not on the same day. Rescue treatment can be initiated at the investigator's discretion at any time during the study if it is in the best interest of the participant. Prior to completion of the Month 12/Study Exit visit, the investigator will be expected to attest to the need for additional nonstudy IOP-lowering (rescue) treatment in the study eye for safety reasons.

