## 7. Discontinuation of Study Intervention and Participant Discontinuation/Withdrawal

A premature discontinuation from study treatment will occur if a participant who signs the ICF and receives study treatment ceases participation in the study, regardless of circumstances, before the completion of the protocol-defined study procedures.

Notification of early participant discontinuation from the study and the reason for discontinuation will be made to the sponsor and will be clearly documented on the appropriate eCRF.

Reasons for discontinuation from the study treatment and/or the study may include the following commonly used or other acceptable terms:

Commonly Used Terms	Other Acceptable Terms
Adverse event Completed Lack of efficacy Lost to follow-up Noncompliance with study drug Other Physician decision Pregnancy Protocol deviation Screen failure Site terminated by sponsor Study terminated by sponsor Withdrawal by subject	Death Failure to meet enrollment criteria Progressive disease Technical problems

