### 7.2. Participant Discontinuation/Withdrawal from the Study

- A participant may withdraw from the study at any time at his/her own request, or may be withdrawn at any time at the discretion of the investigator for safety, behavioral, compliance, or administrative reasons.
- If a participant develops (or has an exacerbation of) a medical condition that, in the opinion of the investigator, would put the participant at an unacceptable medical risk by continuing study participation, the participant will be withdrawn from the study.
- If the participant withdraws consent for disclosure of future information, the sponsor may retain and continue to use any data collected before such a withdrawal of consent.
- If a participant withdraws from the study, he/she may request destruction of any samples taken and not tested, and the investigator must document this in the site study records.

- Participants assigned to and treated with Bimatoprost SR who have received nonstudy IOP-lowering treatment (rescue) in the study eye, will be followed for the duration of the study through the Month 12/Exit visit. If the implant has been removed, the participant may discontinue the study if based on investigator assessment the eye is in stable condition, at which time they should complete the Month 12/Exit visit procedures. Notification of early participant discontinuation from the study and the reason for discontinuation will be made to Allergan and will be clearly documented on the appropriate case report form. If participants discontinue before Month 12/Exit, the site should complete all procedures for the Month 12/Exit visit at the participant's last visit.

The investigator should consider withdrawing a participant from the study early if any of the following criteria are met:

- Participant develops (or has an exacerbation of) a medical condition that, in the opinion of the investigator, compromises the participant's ability to participate in the study
- Participant is unwilling or unable to continue to comply with study procedures
- Participant is unwilling or unable to continue in the study

Whenever possible, the decision to withdraw a participant from the study or study treatment should be discussed with Allergan.

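### The rescue-free Kaplan-Meier curve censors unrescued lack-of-efficacy exits like any other exit, so it is probably too high if any occur; one sensitivity curve would show by how much

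*SAP*

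**What the plan says.** SAP 5.3.4.2 estimates by Kaplan-Meier the time from Bimatoprost SR administration to the first nonstudy rescue treatment in the study eye. Only actual use is an event. For a participant with no rescue, the event "time will be censored at the study exit date or the last visit date if the study exit date is not available". The reason for exit plays no part, and no sensitivity analysis or alternative event definition is given. Protocol 9.4.1.4 adds only that Kaplan-Meier methods will be used.

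Four other places bear on the point:

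- Protocol 7 lists acceptable discontinuation reasons, in a run that reads "Completed Lack of efficacy Lost to follow-up". Appendix 5 defines lack of efficacy.
- Protocol 6.5.3 leaves rescue to the investigator, who may start it "at any time during the study if it is in the best interest of the participant". Inadequate control should first be confirmed at a visit on another day.
- Protocol 7.2 says that Bimatoprost SR participants who have received rescue "will be followed for the duration of the study through the Month 12/Exit visit". It also lets any participant withdraw at any time.
- SAP 5.2 tabulates completion, discontinuation and reasons by cohort. It does not link them to the Kaplan-Meier analysis.

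**The concern.** Kaplan-Meier assumes that a censored eye has the same later risk of rescue as the eyes still under observation. That is reasonable for administrative exits. It is doubtful for a participant who leaves because the treatment did not work and who has not yet started rescue: such an eye probably needs further pressure-lowering treatment sooner than the eyes that stay. Censoring it gives it the course of the eyes doing well enough to remain.

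The design allows this path. Rescue is discretionary, confirmation takes a second visit, and the rule that keeps people to Month 12 covers only those already rescued, who are events anyway. At stake is one estimate that serves the objective "To evaluate the IOP-lowering effect of Bimatoprost SR" (Protocol 3). If the bias is present, it probably flatters the duration of the implant's effect. The disposition table gives the number of such exits, but neither their timing nor how far the curve would move.

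**Working it through.** **Inputs.** SAP 3 gives the cohort size: "Twenty-five to 30 participants will be enrolled in the Bimatoprost SR cohort". The stated target of 20 evaluable participants with up to 33% discontinuation gives 20/(1 − 0.33) = 29.9, so 30. This reproduces the upper end; the lower end of 25 corresponds to 1 − 20/25 = 20% discontinuation. The documents give no expected rescue-free percentage for this trial and no number of unrescued lack-of-efficacy exits, so both are assumed below.

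**Step 1: the gap between the two codings.** Take n eyes. One exits after d1 rescues, d2 rescues follow by Month 12, and there is no other dropout.

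- Exit censored (SAP rule): S = (n − d1)/n × (n − d1 − 1 − d2)/(n − d1 − 1)
- Exit counted as an event: S = (n − d1 − 1 − d2)/n
- Difference = r/n, where r = (n − d1 − 1 − d2)/(n − d1 − 1) is the share of the other eyes at risk at the exit that stay rescue-free to Month 12.

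**Step 2: how the gap relates to bias.** Suppose the leaver would have been rescued by Month 12 with probability p. Full follow-up would then give, on average, (n − d1 − 1 − d2 + 1 − p)/n. The censored estimate equals (n − d1 − 1 − d2 + r)/n. The bias is therefore (p − (1 − r))/n. It is zero if the leaver's risk equals that of the eyes that stayed (p = 1 − r), positive if it is higher, and reaches r/n only at p = 1. So r/n is an upper bound on the bias per exit.

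**Step 3: illustration scaled to the earlier study.** Protocol 2.2.4 reports that more than 66% "were still maintained on monotherapy with the initial Bimatoprost SR implant by Month 6", and that "at least 33% of participants had not received rescue topical IOP-lowering medication or a second Bimatoprost SR administration by Month 12". Reading these as about two thirds and one third, with one exit at Month 6:

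- n = 30, d1 = 10, d2 = 10: r = 9/19 = 0.474. Censored 20/30 × 9/19 = 31.6%; as an event 9/30 = 30.0%; gap 1.6 points.
- n = 25, d1 = 8, d2 = 9: r = 7/16 = 0.438. Censored 17/25 × 7/16 = 29.75%; as an event 7/25 = 28.0%; gap 1.75 points.

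The earlier-study figures are lower bounds, pool all Generation 2 dose strengths, and also count a second implant. They only set a scale.

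**Step 4: assumed illustration.** About half of the eyes are rescued, evenly over Days 60 to 350, with one exit on Day 120, 180 or 270:

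- n = 30 (15 rescued): r = 14/26, 14/23, 14/18; gap 1.8, 2.0, 2.6 points.
- n = 25 (12 rescued): r = 12/21, 12/19, 12/16; gap 2.3, 2.5, 3.0 points.

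**Step 5: ceiling and sampling error.** With r = 1 the gap is 1/30 = 3.3 points or 1/25 = 4.0 points. The standard error at 50% rescue-free is √(0.25/n): 9.1 points (n = 30) or 10.0 points (n = 25). Other early dropout would raise the weight of each remaining eye above 1/n, so these per-exit figures hold only without it.

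**Step 6: more than one exit.** The two codings were also compared with several exits between about Days 113 and 270. In some scenarios about two thirds of eyes were rescued or lost for lack of efficacy by Month 12; in others there were only five rescues. The gap was 1.4 to 3.5 points for one exit, 4.5 to 10.2 for three, and 8.3 to 17.8 for five. Nothing in the documents indicates which count to expect.

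**The case against.** The endpoint is time to initial use. A participant who never used rescue has had no event, and censoring at last observation is the standard rule. That stands, and it is why the main analysis should not change.

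The path is also narrow. Rescue can start at any time, and treatment failure does not require leaving. Uncontrolled pressure is not among the withdrawal criteria in Protocol 7.2. The evidence that lack-of-efficacy exits can occur is a general list of reasons that also contains completion and screen failure. This stands as an argument that such exits may be few or none. It does not exclude them, because no rule requires rescue before exit.

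A single exit moves the curve by less than half a standard error, and a reader could bound the effect at 1/n per exit from the disposition table. That bound is rough: it ignores when the exits occurred and any other dropout.

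A reader might infer more than the documents support:

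- *That the curve must be biased upward.* Recoding an exit as an event can only lower the estimate or leave it unchanged, but bias also requires the leaver's later risk to exceed that of the eyes that stayed. That is plausible, not certain.
- *That the 33% allowance implies many such exits.* It is a planning figure for discontinuation in general, tied to evaluability at Week 8.
- *That the implant gains over LUMIGAN.* Time runs from Bimatoprost SR treatment, so the curve makes no comparison.
- *That unrescued Month 12 completers should be events.* For time to initial use, censoring them is correct.

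**Conclusion.** The point holds in a conditional form and is minor. If any Bimatoprost SR participant discontinues for lack of efficacy before starting rescue, the SAP's censoring is probably informative, and the rescue-free estimate is probably too high from that exit on. The bias per exit is at most r/n: 1.6 to 3.0 points at Month 12 in the illustrations, with a ceiling of 3.3 points (n = 30) to 4.0 points (n = 25). One exit is within sampling error.

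This rests on three assumptions: that at least one such exit occurs, that the leaver's later rescue risk is above that of the eyes that stay, and, for the figures, that there is no other early dropout. The endpoint is descriptive, there are no hypotheses, and the Week 8 primary and secondary results are unaffected.

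**What to change.** Leave the main Kaplan-Meier analysis and all rescue decisions as they are. Before the final database lock, add one sensitivity curve to SAP 5.3.4.2. In it, participants recorded in the disposition data as discontinued (not completed) for lack of efficacy, with no prior rescue in the study eye, count as events on the exit date, or on the last visit date if the exit date is missing. Actual rescues keep their true dates. Show the number of added events beside the curve. If there are none, one sentence saying so replaces it.

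No calendar cut-off is needed, because recorded completion status separates early exits from Month 12 completers. A cut-off would have to choose between the ±14-day visit window and the Month 12 analysis window in SAP Table 6-1, which opens at Day 316.

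The cost is one extra curve from exit reasons already collected, with no new data field. The downside is that the added events rest on an exit reason given by an unmasked investigator, and the second estimate will be the same or less favourable.
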